2.0 Background

2.1 Relevant prior experience and gaps in current knowledge:

Current prosthetic sockets restrict function, lack comfort and cause secondary health problems. Although designed to support the body and enable effective biomechanical load transfer during walking and other activities, prosthetic sockets interface with residual limb tissues that are neither accustomed nor well-suited to

PROTOCOL TITLE: Functional Performance Evaluation of the Northwestern University Flexible Sub-Ischial Vacuum (NU-FlexSIV) Socket for Persons with Transfemoral Amputation

the high pressure and shear loading that occurs during ambulation with a prosthesis. Despite high daily use (>12 hours), lack of socket comfort is the most common complaint of prosthesis users. Prosthetic sockets lead to many issues due to high pressure, shear stress, temperature and moisture, all of which are exacerbated in highly active persons with amputation and those with irregular residual limbs (e.g. due to traumatic amputation that have irregular shape, extensive scarring, invaginations, skin grafts, painful neuromas, etc.). Residual limb skin problems include cysts, calluses, verrucous hyperplasia, allergic reactions, and bacterial or fungal infections. Residual limb skin problems have been reported by 25% to 63% of persons with amputation in the general population and problems have a negative influence on ability to perform household tasks, prosthesis use, social functioning, and participation in sports.

Sub-ischial sockets challenge conventional understanding of the biomechanics of transfemoral sockets, especially regarding coronal plane stability. In able-bodied walking, the hip abductors, primarily the gluteus medius, maintain pelvic control during single limb stance. Contraction of the hip abductors counters the moment created about the hip by the body center of mass and helps to keep the pelvis level and trunk upright. When the abductors are compromised, lateral trunk lean over the stance limb may be observed (often referred to as a Trendelenberg gait). In the IC socket, skeletal contact over the medial aspect of the ischium and greater trochanter, create a medial-lateral ‘skeletal lock’ for coronal plane control. For sub-ischial sockets, these forces still remain but the socket geometry believed necessary to control them is gone.

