The mechanism by which transfemoral prosthetic sockets provide coronal plane stability during gait has been recently debated. Dillon (2007) stated that in an IC socket coronal plane pelvic stability is derived almost entirely from containment of the ischium and ischial ramus and that when containment is not achieved, coronal plane stability is poor. Dillon (2007) has also argued that the ability of any socket to provide coronal plane stability relies in part on the soft tissue, especially the adductors, being compressed to increase stiffness. Compression of soft tissues may occur to a larger extent when vacuum-assisted suspension is used because both the liner and socket are considerably under-sized, potentially contributing to coronal plane stability.

In contrast to existing transfemoral sockets, the NU-FlexSIV Socket does not impinge on the pelvis because it has lower proximal trim lines; is highly flexible allowing muscles to move comfortably within the socket as they contract during activity and improving sitting comfort; and is held securely to the residual limb by suction from a vacuum pump as well as compression from the liner and socket being undersized, making for a firmer connection to the prosthesis.

PROTOCOL TITLE: Functional Performance Evaluation of the Northwestern University Flexible Sub-Ischial Vacuum (NU-FlexSIV) Socket for Persons with Transfemoral Amputation

2.2 Relevant preliminary data:

Our technique requires specific rectifications of the positive model which we have quantified using rectification mapping (Figure 1).

[figure not shown]

Figure 1 Modification pattern averaged across 30 pairs of rectified and unrectified casts of transfemoral residual limbs.

Preliminary tests of individuals using sub-ischial sockets illustrate that they do not use significant trunk lean during walking (Figure 2).

[figure not shown]

Figure 2 Midstance posture of subject wearing a sub-ischial socket (a). Lateral trunk flexion data comparing IC and sub-ischial sockets (b).

PROTOCOL TITLE: Functional Performance Evaluation of the Northwestern University Flexible Sub-Ischial Vacuum (NU-FlexSIV) Socket for Persons with Transfemoral Amputation

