9.0 Procedures Involved

9.1 Study design:

The clinical trial will be an assessor-blinded prospective randomized cross-over trial wherein participants with unilateral transfemoral amputation will be randomized to using one of two socket conditions (i.e., sub-ischial or ischial containment) before crossing over to the other socket condition. Random allocation (computer-generated) utilizing blocks of random size will be used to assign the initial treatment condition. The trial will be balanced such that all subjects will receive all treatments (i.e., both socket conditions) and that all subjects will participate for the same number of periods (i.e., two).

9.2 Research procedures:

The study is composed of two phases for each socket: socket preparation and then 6 weeks of socket wear during which 3 identical data collection sessions will be held (week 1, 3 weeks and 6 weeks).

Socket Preparation Phase:

All sockets will be made following standard clinical procedures that include taking an impression (i.e., cast) of the residual limb, converting the negative residual limb model to a positive mold made of plaster of Paris, rectifying the positive mold using the rectification procedures specific to each socket design, thermoforming a clear diagnostic check socket, and ultimately manually fabricating, fitting and aligning a definitive socket.

Data Collection:

At each visit we will collect the following data:

1. *Socket Comfort Score (SCS)* – The SCS is a simple rating of comfort on a scale of 0 to 10 where 0 is the most uncomfortable socket fit imaginable and 10 is the most comfortable socket fit.
2. *Orthotic and Prosthetic Users' Survey (OPUS)* – The OPUS is a set of surveys that evaluate the subject's perception of function, quality of life, and satisfaction with the socket and prosthesis. The lower extremity function survey has 20 questions rated on a 5-point scale; the quality of life survey has 23 questions rated on a 5-point scale; and the satisfaction with device survey has 9 questions rated on a 5-point scale.

PROTOCOL TITLE: Functional Performance Evaluation of the Northwestern University Flexible Sub-Ischial Vacuum (NU-FlexSIV) Socket for Persons with Transfemoral Amputation

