11.0 Data and Specimen Management

11.1 Data analysis:

Before analyses begin, all variables will be plotted using histograms to inspect the shape of distributions and to check for outliers. We will not drop cases nor transform variables but if we identify any possibility that assumptions have been violated, we will employ alternative analysis approaches. As part of data screening, we will describe the amount of data that are missing, and we will compare participants with and without missing data.

Hypothesis 1: We hypothesize that the NU-FlexSIV Socket will provide increased comfort compared to the ischial containment socket.

Our primary end point is Socket Comfort Score at 6 weeks, which has been reported to have a sensitivity to socket change of 1 to 3 points (Hanspal, Fisher et al. 2003). Additionally, it has been argued that the Socket Comfort Score may be considered a continuous variable, and therefore suitable for parametric analysis, given the large number of ordered categories and the linear nature of changes in socket comfort with different configurations of socket conditions (Fatone, Dillon et al. 2015). Hence, a matched pairs t-test ($\alpha=0.05$) will be used to assess the primary outcome, Socket Comfort Score.

Hypothesis 2a: We hypothesize that the NU-FlexSIV Socket will allow greater prosthetic side hip range of motion, in particular increased hip extension, leading to increased prosthetic side step length and hence walking speed compared to the ischial containment socket.

Hypothesis 2b: We hypothesize that step width and lateral trunk flexion over the prosthetic limb will not differ between the NU-FlexSIV Socket and ischial containment socket.

For these secondary hypotheses, data analysis will include the following gait variables: walking speed (m/s), step width (m), step length (m), sagittal plane hip range of motion (degrees), maximum hip extension (degrees), and lateral trunk lean over the prosthetic limb during stance (degrees). A multiple analysis of variance (MANOVA, $\alpha=0.05$) will be used to compare gait variables across socket conditions as it is the most rigorous approach given the relationship that exists between these dependent variables (e.g., walking velocity and step length are correlated). The challenge of this approach is being convinced that underlying assumptions are met.

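### Hypothesis 2b predicts no difference in step width and trunk flexion, but its only test is a six-variable difference-seeking MANOVA shared with 2a, and no result of that test can support it

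*Combined protocol and SAP*

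**What the plan says.** Sections 1.2 and 11.1 state Hypothesis 2b as a prediction that "step width and lateral trunk flexion over the prosthetic limb will not differ between the NU-FlexSIV Socket and ischial containment socket". Hypothesis 2a, stated just before it, predicts differences: more hip motion, longer prosthetic-side steps and faster walking.

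Section 11.1 handles the two together. "For these secondary hypotheses, data analysis will include the following gait variables": walking speed, step width, step length, sagittal hip range of motion, maximum hip extension and lateral trunk lean. Four of these belong to 2a. Step width and trunk lean belong to 2b. One MANOVA at alpha 0.05 "will be used to compare gait variables across socket conditions as it is the most rigorous approach". The only fallback is an unnamed alternative analysis if assumptions appear violated.

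On timing, section 9.2 says "3 identical data collection sessions will be held (week 1, 3 weeks and 6 weeks" in each socket. Section 11.1 fixes a time point for one outcome only: "Our primary end point is Socket Comfort Score at 6 weeks".

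**The concern.** The null hypothesis of the MANOVA is no socket difference on all six variables jointly. Hypothesis 2b is part of that null, and a significance test can reject a null but cannot establish it. Pooling 2b with 2a adds a second fault: a rejection cannot be assigned to, or away from, the two 2b variables.

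2b is the hypothesis that covers the coronal-plane measures. Section 2.1 says of that plane: "For sub-ischial sockets, these forces still remain but the socket geometry believed necessary to control them is gone". It also says, about able-bodied walking, "When the abductors are compromised, lateral trunk lean over the stance limb may be observed". Linking those two statements to 2b is our inference. As written, a non-significant MANOVA could be reported as confirming that the new socket leaves step width and trunk lean unchanged.

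**Working it through.** **The logic, which needs no figures**

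| MANOVA result | For 2a (difference) | For 2b (no difference) |
|---|---|---|
| Significant | Some combination of the six differs; which is unknown | Cannot be assigned to, or away from, step width and trunk lean |
| Not significant | Not supported | Not shown: absence of evidence only |

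No row supports 2b. Per-variable t-tests are a common follow-up, but none is stated, and a non-significant t-test does not show sameness either.

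**The plan's own figure.** Section 11.2 gives 25 subjects for a two-tailed paired t-test on Socket Comfort Score (d = 0.754, alpha 0.05, power 0.95). Noncentral-t power is 0.942 at n=24 and 0.951 at n=25, so 25 reproduces. No sample size or power is given for 2a or 2b.

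**Inputs for the illustration.** From the documents: six variables, alpha 0.05, 25 completers needed and 35 recruited (sections 11.2 and 23.3). Assumed, because the documents give none: effects in SDs of the paired socket difference, correlations among the differences, and margins. There is one paired difference per variable at one time point. The n=35 figures assume no attrition.

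1. **Chance of missing a real shift.** With two conditions in the same subjects, the MANOVA is Hotelling's T² on six paired differences. This follows a noncentral F on 6 and n − 6 df with noncentrality λ = n·μ′R⁻¹μ. One variable is shifted 0.5 SD and the other five are at 0.
   - Correlation 0, n=25: λ = 25 × 0.25 = 6.25.
   - Equal correlation 0.7: the diagonal element of R⁻¹ is (1 + 4 × 0.7)/(0.3 × (1 + 5 × 0.7)) = 3.8/1.35 = 2.815, so λ = 6.25 × 2.815 = 17.59.

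   | Equal correlation | Missed, n=25 | Missed, n=35 |
   |---|---|---|
   | 0 | 0.690 | 0.524 |
   | 0.3 | 0.611 | 0.414 |
   | 0.5 | 0.477 | 0.255 |
   | 0.7 | 0.228 | 0.061 |

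2. **Rejection when 2b is exactly true.** All four 2a variables are shifted 0.5 SD and both 2b variables are at 0, n=25. With independent variables λ = 25 × 4 × 0.25 = 25, and simulation (20,000 replicates) rejects 91% of the time. With correlation 0.5 among the 2a variables it rejects 49%. If both 2b variables are also shifted 0.5 SD, it rejects 99% and 88%. A rejection therefore comes often whether 2b is true or false.

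3. **A single paired t-test** on a 0.5 SD shift (two-sided 0.05) has power 0.670 at n=25 and 0.820 at n=35. It misses 33% and 18% of the time.

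4. **What estimation would deliver.** The 95% CI half-width is t(0.975, n − 1)/√n: 2.064/5 = 0.41 SD at n=25 and 2.032/5.916 = 0.34 SD at n=35.

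5. **What an equivalence claim would need.** Two one-sided tests at 5% (90% CI inside the margin), true difference 0. Joint power is for two independent variables.

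   | Margin | n | Power per variable | Joint power |
   |---|---|---|---|
   | 0.5 SD | 25 | 0.567 | 0.567² = 0.32 |
   | 0.6 SD | 25 | 0.796 | 0.796² = 0.63 |
   | 0.5 SD | 35 | 0.790 | 0.790² = 0.62 |
   | 0.6 SD | 35 | 0.933 | 0.933² = 0.87 |

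   A wide margin lets real shifts through. At 0.75 SD and n=25, with one variable truly shifted 0.3 SD (passes 0.705) and the other at 0 (passes 0.954), both pass 0.705 × 0.954 = 0.67 of the time.

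**The case against.** - **Weight.** 2b is part of a secondary hypothesis, no decision in the plan depends on it, and the harm arises only if someone misreads a non-significant result. All true, and it limits the severity. It does not give 2b a valid test.
- **Prior evidence.** Section 2.1 offers a compression mechanism ("both the liner and socket are considerably under-sized, potentially contributing to coronal plane stability"), section 2.2 reports preliminary tests without significant trunk lean, and section 2 also describes a ten-person cross-over trial that found gait and balance equivalent between ischial containment and brimless sockets. This makes 2b plausible. It does not replace an analysis of 2b in this trial.
- **Time point.** Section 11.4 presents the earlier sessions as a resource if a subject cannot wear a socket for the full six weeks, which suggests that 6 weeks is the intended gait comparison. That narrows the ambiguity, but no sentence fixes it. The gap is not peculiar to 2b: the timed tests and the OPUS share it.
- **Illustrative figures.** The miss rate at n=25 runs from 69% to 23% on an unknown correlation alone, in a scenario where 2a is wholly false. The range is too wide to serve as an estimate, and the conclusion does not use it as one.
- **Leaving the 2a test alone.** If step width and trunk lean stay in the MANOVA, a shift in them could produce a rejection credited to 2a. This stands, but it is a separate choice about 2a.
- **Rewriting 2b.** The sponsor may prefer margins to an estimation aim. Either is acceptable if set in advance.

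**Conclusion.** The concern holds. The plan states a hypothesis of no difference and assigns it to a test whose significant result cannot be attributed to the two relevant variables and whose non-significant result is not evidence of sameness. This is an error in the analysis as written, not a missing detail, and it depends on no assumed number. The calculations show only that the gap could matter at 25 to 35 subjects: under the stated assumptions, a 0.5 SD shift in one variable goes undetected by the MANOVA 6% to 69% of the time, depending on sample size and correlation. It should be fixed. The primary Socket Comfort Score test and the sample size of 25 are untouched.

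**What to change.** In sections 1.2 and 11.1:

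1. Take 2b out of the MANOVA's inference.
2. Report the paired socket difference in step width (m) and in lateral trunk lean (degrees), each with a 95% CI, at one stated time point.
3. Restate 2b as an estimation aim, and say that a non-significant test will not be read as no difference.
4. Only if the sponsor wants to claim no relevant difference: before data are analysed, set a margin for each variable, justified by relevance and not by power, and require both 90% CIs to lie inside their margins.

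The cost is wording. No new data or subjects are needed, and the MANOVA for 2a need not change. With estimation the trial gives up a conclusion of no difference, which the present plan could not validly reach, and the intervals may be wide. With margins, equivalence on both variables may well not be shown at this sample size.

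Cutting the 2a MANOVA to its four variables is optional and can go either way. With all four shifted 0.6 SD, 2b true and n=25, power falls from 0.963 to 0.784 if all six variables correlate at 0.5, but rises from 0.671 to 0.784 if only the 2a variables do.

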1.0 Objectives

1.1 Specific aims:

This proposal aims to provide evidence to support use of the NU-FlexSIV Socket for persons with transfemoral (above-the-knee) amputation. This will be accomplished by undertaking a prospective, assessor-blinded randomized cross-over trial comparing comfort and functional performance with the NU-FlexSIV Socket to the standard-of-care ischial containment socket in persons with unilateral transfemoral amputation.

The primary aims of the study are:

Aim 1: To demonstrate if the NU-FlexSIV Socket is more comfortable than the IC socket.

Aim 2: To demonstrate if the NU-FlexSIV Socket results in better functional performance than the IC socket.

Aim 3: To demonstrate the NU-FlexSIV Socket will result in better quality of life and “satisfaction with device” (i.e. prosthesis) than the IC socket.

1.2 Hypotheses to be tested:

Hypothesis 1: We hypothesize that the NU-FlexSIV Socket will provide increased comfort compared to the ischial containment socket.

Hypothesis 2a: We hypothesize that the NU-FlexSIV Socket will allow greater prosthetic side hip range of motion, in particular increased hip extension, leading to increased prosthetic side step length and hence walking speed compared to the ischial containment socket.

Hypothesis 2b: We hypothesize that step width and lateral trunk flexion over the prosthetic limb will not differ between the NU-FlexSIV Socket and ischial containment socket.

Hypothesis 2c: We hypothesize that the NU-FlexSIV Socket will result in faster times to perform the 5-Times Rapid Sit-to-Stand Test, Four Square Step Test and T-Test of Agility compared to the ischial containment socket.

Hypothesis 3: We hypothesize that the NU-FlexSIV Socket will result in better health-related quality of life and satisfaction with device as assessed using the OPUS compared to the ischial containment socket.

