Hypothesis 2c: We hypothesize that the NU-FlexSIV Socket will result in faster times to perform the 5-Times Rapid Sit-to-Stand Test, Four Square Step Test and T-Test of Agility compared to the ischial containment socket.

PROTOCOL TITLE: Functional Performance Evaluation of the Northwestern University Flexible Sub-Ischial Vacuum (NU-FlexSIV) Socket for Persons with Transfemoral Amputation

The difference in these timed performance tests across socket conditions will be tested using repeated measures t-tests with alpha=0.05 which will be adjusted using the Bonferroni correction to account for Type 1 error.

Hypothesis 3: We hypothesize that the NU-FlexSIV Socket will result in better health-related quality of life and satisfaction with device as assessed using the OPUS compared to the ischial containment socket.

The OPUS uses Likert scale responses for each item of each module. However, these responses can be converted into a single score for each module. If assumptions of normality are met, analysis with parametric procedures can be used to assess differences in module scores between sockets. Hence, we will use repeated measures t-tests with alpha=0.05 which will be adjusted using the Bonferroni correction to account for Type 1 error.

11.2 Power analysis:

To determine a sample size estimate, we have utilized data obtained from a previous pilot study.⁴⁴ In that study, we collected Socket Comfort Scores from six persons with unilateral transfemoral amputation wearing an ischial ramal containment socket and the same socket with a wider medio-lateral dimension (effect size, $d = 0.754$). Using the G*Power computer program, this effect size was used to estimate sample size. This data was used because we do not have pilot data for this particular study design. For a 2-tailed matched pairs t-test we would need a total sample size of 25 to detect an effect size of 0.754 with a critical alpha of 0.05 and power of 0.95. In order to account for possible attrition in subject numbers we will recruit 35 persons with unilateral transfemoral amputation.

11.3 Steps to be taken to secure the data to maintain confidentiality during storage, use, and transmission:

All personnel involved with the study have or will complete IRB required training.

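### The only planned test of Hypothesis 2a is a non-directional six-variable MANOVA, which cannot show that hip motion, step length or walking speed improved

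*Combined protocol and SAP*

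**What the plan says.** Section 1.2 states Hypothesis 2a as a chain of signed claims about the new design, which is expected to "allow greater prosthetic side hip range of motion, in particular increased hip extension, leading to increased prosthetic side step length and hence walking speed". Hypothesis 2b predicts the opposite kind of result for two other variables, namely that "step width and lateral trunk flexion over the prosthetic limb will not differ" between sockets.

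Section 11.1 repeats both hypotheses and gives them one joint analysis. Six gait variables (speed, step width, step length, sagittal hip range of motion, maximum hip extension, trunk lean) enter a MANOVA at alpha 0.05 that "will be used to compare gait variables across socket conditions as it is the most rigorous approach". The reason given is that the outcomes are related, for example that "walking velocity and step length are correlated". No univariate test, direction or decision rule follows. The only fallback is general: "if we identify any possibility that assumptions have been violated, we will employ alternative analysis approaches".

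For Hypothesis 2c, and in the same terms for Hypothesis 3, the section instead plans "repeated measures t-tests with alpha=0.05 which will be adjusted using the Bonferroni correction".

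**The concern.** A MANOVA asks whether the vector of six mean differences is zero. Hypothesis 2a asks whether four particular components are positive. These are different questions in two respects:

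- **Direction.** The statistic is a quadratic form in the differences, so reversing every sign leaves it unchanged.
- **Attribution.** Rejection can come from any of the six variables, including the two that the protocol expects not to change.

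Aim 2, better functional performance, rests partly on 2a. With no signed or per-variable rule in the plan, the way from the MANOVA p-value to a statement about hip extension or speed would have to be chosen after the data are seen. Whether the MANOVA is a suitable test of the no-difference claim in 2b is a separate matter and is not argued here.

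**Working it through.** **The plan's own figure.** Section 11.2 sizes the trial on the Socket Comfort Score: two-sided matched pairs t-test, d = 0.754, alpha 0.05, power 0.95. With noncentrality 0.754 × √25 = 3.77 on 24 df, power is 0.951; with n = 24 it is 0.942. So 25 reproduces. No power is stated for the gait MANOVA.

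**Inputs.** From the documents: six variables, alpha 0.05, 25 completers (sections 11.2 and 23.3). Assumed, because the documents do not give them: one paired difference per variable per subject, a within-subject test, standardised shifts d, and correlations r among the paired differences.

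**Formula.** With two conditions within subject, the MANOVA is Hotelling's T² on the six paired differences. It is referred to F with 6 and 25 − 6 = 19 df (5% critical value 2.63), with noncentrality λ = n δ′R⁻¹δ, where δ is the vector of shifts and R their correlation matrix.

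**Step 1, direction.** Replacing δ by −δ leaves λ unchanged. If the four 2a variables shift by 0.5 SD with r = 0.5 among them, and the two 2b variables neither shift nor correlate with them, then λ = 25 × 4 × 0.25 / (1 + 3 × 0.5) = 10. The rejection probability is 0.49, whether all four improve or all four worsen. At 0.754 SD it is 0.88 either way. The equality holds for every effect size and correlation.

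**Step 2, attribution.** Suppose only step width moves, by 0.8 SD.

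- Step width uncorrelated with the rest: λ = 25 × 0.64 = 16, rejection probability 0.72.
- Correlation 0.3 shared by all six: λ = 20.1, probability 0.83.
- Correlation 0.5 shared by all six: λ = 16 × 3 / (0.5 × 3.5) = 27.4, probability 0.94.

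In each case no 2a variable has changed.

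**Step 3, power when 2a is true.** All four 2a variables improve by 0.5 SD, the two 2b variables do not change, n = 25. The Holm columns are simulated paired t-tests on the four 2a variables.

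| r | MANOVA, 2b variables uncorrelated with 2a variables | MANOVA, all six share r | Holm, at least one of four | Holm, all four |
|---|---|---|---|---|
| 0.3 | 0.63 | 0.80 | 0.82 | 0.27 |
| 0.5 | 0.49 | 0.86 | 0.76 | 0.33 |
| 0.7 | 0.40 | 0.97 | 0.68 | 0.39 |

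Which approach has more power depends on how the 2b variables correlate with the 2a variables, which the documents do not report. It depends on effect size too. With the 2b variables uncorrelated, MANOVA power runs from 0.14 (d = 0.3, r = 0.8) to about 1.00 (d = 0.754, r = 0).

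**The case against.** The strongest defence is that the choice is reasoned. Section 11.1 justifies the MANOVA by the correlation among gait variables, admits that its assumptions are a challenge and allows for alternatives. These hypotheses are secondary. The sample size and main conclusion rest on the Socket Comfort Score, and Aim 2 also draws on the Bonferroni-adjusted tests of 2c. Analysts would see the signed means in any case. All of this is fair and limits the weight of the point. It does not supply what is missing: handling correlation gives no direction, the alternatives are unnamed and apply only if assumptions appear violated, and reading signs off means without a rule is not a planned test.

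A reader might infer three stronger things that the documents do not support.

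- **That the plan counts a significant MANOVA as support for 2a, even if gait worsens.** It does not say so. The decision rule is absent rather than wrong.
- **That the MANOVA has low power when 2a is true.** The documents give no gait effect size, SD or correlation, and the table above runs from 0.40 to 0.97 at a single effect size. The 0.754 in section 11.2 is a comfort-score effect from six persons in a different socket comparison, so it does not settle the matter either way.
- **That false positives are inflated.** If analysts added unadjusted follow-up t-tests after a significant MANOVA, and only step width had moved by 0.8 SD, about 15% to 16% of trials would wrongly flag at least one 2a variable. The plan proposes no such tests, so this figure describes a hypothetical procedure.

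**Conclusion.** The point stands as a mismatch between hypothesis and test. The one analysis planned for 2a cannot establish that any of its four variables improved, and the plan has no signed, multiplicity-controlled per-variable rule to do so. The blindness to sign needs no assumption about effect size or correlation. The probability of about 0.72 to 0.94 for a significant result driven by step width alone assumes 25 completers, a within-subject test, a 0.8 SD shift, and correlation from 0 to 0.5 shared by all six variables (0.72 if step width is uncorrelated with the rest). What can be said about power is only that the plan does not justify it for 2a. The change should be made, but it concerns a secondary hypothesis and leaves the primary analysis untouched.

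**What to change.** In section 11.1, make the confirmatory analysis of 2a four within-subject paired tests: sagittal hip range of motion, maximum hip extension, step length and walking speed. Adjust across the four by Holm, or by the Bonferroni correction already used for 2c and 3, at a two-sided family level of 0.05. Report each as a signed mean difference with a confidence interval. State that 2a is supported for a variable only if the adjusted p is below 0.05 and the sign favours the NU-FlexSIV Socket. Take step width and trunk lean out of the 2a test. The MANOVA may stay as a descriptive supplement.

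The change needs wording only and no new data. It does have a price. The strictest per-variable threshold is 0.05 / 4 = 0.0125. The MANOVA can be more powerful under some correlation patterns (at d = 0.5 and r = 0.7 shared by all six, 0.97 against 0.68 for at least one variable by Holm). Support on all four variables, which the full chain in 2a would need, is unlikely at modest effects: about 0.27 to 0.39 with Holm at d = 0.5 and r = 0.3 to 0.7.
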